### **7.3. Reporting procedures**

#### **7.3.1. Serious adverse events**

All SAEs occurring within 28 days post booster dose must be reported to both the local data safety and monitoring board (DSMB) and the Sponsor, even if the investigator considers that the SAE is not related to treatment. Reporting procedures to the local DSMB will follow established icddr,b policy, whereas reporting to the Sponsor will be described in detail in an SOP. To report to the Sponsor, the study clinician will complete a Serious Adverse Event Form within the following timelines of such events:

- All SAEs, regardless of relationship, will be recorded on the Serious Adverse Event Form and sent by email to the Sponsor and the contract research organization within 24 hours of site awareness, as outlined in a reporting SOP.

SAEs reported to the local DSMB will be reviewed by the committee as per established icddr,b guidelines and will be reviewed during the scheduled meetings between the icddr,b, DSMB, and the PI. Details for how review of SAEs and other unanticipated problems will be conducted will be contained in an SOP.

#### **7.3.2. Regulatory reporting**

Collected SAEs will be reported to responsible ethical review committees according to requested timelines. Collected local and systemic reactions and adverse events not meeting the criteria of an SAE will be summarized at the end of the study, and a summary report will be sent to responsible ethical review committees and CDIBP manufacturers.

### **7.4. Safety monitoring plan**

#### **7.4.1. Post vaccination follow-up**

Parents of children will be advised about possible short-term mild reactogenicity that may occur post vaccination. Parents will have the contact numbers of the study physician and community health workers. The parent will also be reminded to contact the study team if the child experiences any illness, has received any medical care, or requires any medical care. The Sponsor and the Ethical Review Committee (ERC) will be notified within 24 hours of any SAEs.

#### **7.4.2. Data and safety monitoring board**

An independent, local DSMB will be constituted to monitor all SAEs. The DSMB chair will review all SAEs occurring 28 days post vaccination, including deaths. The DSMB will be instructed to use their clinical judgment in order to provide guidance or recommendations for stopping the study early due to a safety concern. The DSMB will evaluate the safety data from these children including SAEs. In addition, the DSMB will be asked to review in real time all SAEs suspected to be related to the product and provide recommendations to the icddr,b and PATH teams.

### **7.5. Halting rules**

Given the experience with CD-JEV, no safety issues are anticipated which would result in the suspension of the study. However, the trial might be suspended at any time by PATH, the local DSMB, or any ethical review committee overseeing this study for any safety concern. This includes, for example, and without limitation, an SAE resulting in death, an unexpectedly high number of persons experiencing a similar event after receipt of any dose, or an unusually high rate of SAEs. PATH may suspend the study in the event that study conduct is found to be below GCP standards.

Should an SAE occur which is likely related to administration of study vaccine, the decision whether the study should continue per protocol, proceed with caution, be suspended pending further investigation, be discontinued, or be modified and then proceed will be made by PATH in consultation with the investigators, the DSMB, and/or the icddr,b Research Review Committee (RRC) and ERC. However, no rules will be prespecified to define these conditions.

If the study is halted, participants will be contacted immediately explaining why the study has been halted and the implications for their medical well-being.

In the event of the appearance of new data that indicate an increased level of risk to participants, the clinical trial will be suspended until PATH, the DSMB, and all ethical review committees have reviewed relevant data and agreed that the trial may proceed.

## **7.6. Data handling and record keeping**

### **7.6.1. Data management responsibilities**

The PI is responsible for ensuring the accuracy, completeness, legibility, and timeliness of the data reported. All source documents will be completed in a neat, legible manner in black ink to ensure accurate interpretation of data and clarity of reproduced copies. The study workers will be asked not to erase, overwrite or use correction fluid or tape on the original. An SOP will be available providing details of data management responsibilities.

All source documents and laboratory reports will be reviewed by the clinical team and data entry staff, who will ensure that they are accurate and complete. Data collection will be the responsibility of the clinical trial staff at the site under the supervision of the PI. During the study, the PI will maintain complete and accurate documentation for the study and will advise and oversee local investigators who will conduct data management, entry, and quality review. Analysis and reporting of study data will be done by the trial statistician after data lock.

### **7.6.2. Data capture methods**

Clinical data and laboratory data will be recorded on CRFs. All children will be assigned a unique study participant number at study enrollment; this study participant number will be included on all forms and in the computer database and will serve to link study data to specific individuals. Data forms will be verified for accuracy, linked by study participant number, and managed using database management software (yet to be determined).

### **7.6.3. Study records**

In accordance with applicable regulatory requirements, following closure of the study, the investigator/institution will maintain a copy of study documents in a secure and designated location at the study site. Essential documents shall be retained for at least five years after the completion or discontinuation of the study.

No records will be destroyed without the written consent of PATH. It is the responsibility of PATH to inform the PI when these documents no longer need to be retained.

Study data collection forms (i.e., CRFs), informed consent documents, and adverse event-related medical records are the primary source documents for this study. Only authorized study staff and representatives of the monitoring team, the sponsor, independent ethical committee, and data monitoring committee and appropriate regulatory agencies may have direct access to source documents containing study data.

#### **7.6.4. Protocol deviations**

A protocol deviation is any noncompliance with the clinical trial protocol, GCP, or Manual of Procedures requirements. The noncompliance may be either on the part of the child or parent, the investigator(s), or the study site staff. As a result of deviations, corrective actions are to be developed by the site and implemented promptly.

It is the responsibility of the site to use continuous vigilance to identify and report deviations within five working days of identification of the protocol deviation, or within five working days of the scheduled protocol-required activity. All deviations will be promptly reported to PATH.

A completed copy of the Protocol Deviation Form will be maintained in the regulatory file. Protocol deviations will be sent to the local IRB/ERC per their guidelines. The PI and study staff are responsible for knowing and adhering to their IRB/ERC requirements.

#### **7.7. Quality control and quality assurance**

The study will be conducted in accordance with procedures identified in the protocol and SOPs. SOPs will be developed and revised as necessary. In addition, monitoring plans, data management plans, and quality management plans will be developed.

Site monitoring will be conducted to ensure that human subject protection, study procedures, laboratory procedures, study intervention administration, and data collection processes are of high quality and meet sponsor, International Conference on Harmonisation (ICH) GCP, and regulatory standards, and that the study is conducted in accordance with the protocol and SOPs.

All site staff will be required to have training in GCP, informed consent, and protocol implementation prior to work on the project. All study staff, including temporary staff such as nurses, phlebotomists, and interviewers will attend mandatory training prior to participant enrollment.

#### **7.8. Clinical monitoring**

##### **7.8.1. Site monitoring plan**

Qualified and appropriately trained individuals from PATH or designated by PATH will carefully monitor the study. The study monitor will periodically contact the site and perform on-site visits. The extent, nature and frequency of site visits will be based on such considerations as study objectives, study design and complexity, and enrollment rate; periodicity and nature of monitoring activities will be described in the Monitoring Plan. PATH may also include representatives of the Bill & Melinda Gates Foundation (The Foundation) in site contacts and visits, as appropriate, and will keep The Foundation program officer apprised of study progress.

##### **7.8.2. Site initiation visit**

A site initiation visit will occur prior to approval to initiate the study. The study monitor and/or PATH representatives will verify and document that the study team has been properly informed about the trial, the materials to be used during the trial have been received and are appropriately stored, regulatory requirements are met and documented, and that approved study SOPs are in place. Prior to enrollment of participants at the study site, specific regulatory documents must be available, such as independent ethics committee (IEC) approvals, other IRB required approvals, and curriculum vitae for investigator and study staff.

##### **7.8.3. Follow-up visits**

Monitoring will be conducted according to PATH's requirements. The individuals responsible for monitoring the study will periodically review the progress of the study and should have access to all records necessary to ensure the ethical and safety conduct of the study and the integrity/validity of the recorded data.

During site visits and contacts, the monitor will:

- Check and assess the progress of the study.
- Review study data collected.
- Perform source data verification.
- Review trial master files for essential documents.
- Evaluate adherence to standard operating procedures.
- Identify any issues and address their resolution.

This will be done in order to verify that:

- The data are authentic, accurate, and complete.
- The safety and rights of participants are protected.
- The study is conducted in accordance with the approved protocol (and any subsequent amendment) and all applicable regulatory requirements.

As part of study conduct, the investigator agrees to allow the monitor or PATH representative direct access to all relevant documents and to allocate time to the monitor to discuss findings and any relevant issues. The investigator also agrees to allow representatives of the Foundation, authorized by PATH, to occasionally accompany the monitor or PATH representative during site visits.

#### 7.8.4. Close-out visit

Upon completion of the study, the study monitor or PATH representative and the investigator will conduct the following activities:

- Data clarification and/or resolution.
- Accounting, reconciliation, and destruction at sites of used and unused vaccines.
- Review of site study records for completeness.
- Return copy of study data to PATH.

PATH and any regulatory body retain the right to temporarily suspend or prematurely discontinue this study at any time related to safety. If the study is stopped or suspended prematurely, PATH will inform the investigator as well as regulatory authorities about the decision and the reasons for termination or suspension. If such action is taken, all efforts must be made to ensure the safety of the participants enrolled in the study. The investigator will inform the responsible IEC and provide the reason for the suspension or termination. In case of premature study or study site closure, the monitor or PATH representative will conduct all activities as indicated above.

#### 7.8.5. Allowable schedule of study visits

For clarity, per-protocol timing of key study visits is provided below in Table 4. No child should be dropped from the study solely on the basis of a visit falling outside of an allowable time-frame for that visit if there is good faith attempt by study staff and the child participant's parent(s)/guardian(s) to adhere to the protocol.

**Table 4. Allowable Schedule**

Study Visit	Should occur	May occur
Visit 01	Three years after initial vaccination	Three years $\pm$ 3 months after initial vaccination
Visit 02	Day 365	One year $\pm$ 28 days after Visit 01
Visit 03	Day 366	1 day after booster vaccination
Visit 04	Day 367	2 days after booster vaccination
Visit 05	Day 368	3 days after booster vaccination
Visit 06	Day 369	4 days after booster vaccination
Visit 07	Day 370	5 days after booster vaccination

Study Visit	Should occur	May occur
Visit 08	Day 371	6 days after booster vaccination
Visit 09	Day 372	7 to 10 days after booster vaccination
Visit 10	Day 393	21 to 35 days after booster vaccination

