#### **2.4. Outcome measures**

The immunologic endpoints will be:

- Seroprotection rate defined as the proportion of study participants with an anti-Japanese encephalitis (JE) neutralizing antibody titer  $\geq 1:10$  as measured by 50% plaque reduction neutralization test (PRNT-50).
- Geometric mean titer (GMT) of anti-JE neutralizing antibody as measured by PRNT-50.

The safety endpoints will be:

- Frequency counts and percentage of participants reporting immediate unsolicited adverse events (AEs) occurring within 30 minutes of booster vaccination.
- Frequency counts and percentage of participants reporting solicited local and systemic AEs occurring within 7 days of booster vaccination.
- Frequency counts and percentage of participants reporting unsolicited AEs and serious adverse events (SAEs) occurring within 28 days of booster vaccination.

The exploratory immunologic endpoint will be:

- Proportion of participants with demonstrated seropositivity for anti-JE immunoglobulin M (IgM) prior to the booster dose and 7 days post booster dose as measured by enzyme-linked immuno assay (ELISA). Seropositivity will be defined per the ELISA manufacturer's kit instructions.

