## 4. RESEARCH DESIGN AND METHODS

The proposed study is a phase 4 open-label trial enrolling up to 818 Bangladeshi children who had previously participated in JEV05, a PATH-supported clinical study conducted from May to December 2012 during which 10- to 12-month-old infants were given a single dose of CD-JEV. Eligible JEV05 participants who still live in the

area will be identified using the local health and demographic surveillance system (HDSS) and asked to participate. Children will be divided into two groups based on whether they received vaccine from the old or new facility in JEV05:

- Group A (up to 655 eligible): children randomized to Groups 2-4 (new facility) in JEV05.
- Group B (up to 163 eligible): children randomized to Group 1 (old facility) in JEV05.

An overview of the study activities is provided in Table 3. A 2 ml blood sample will be collected from all participants three and four years after initial vaccination. The sera will be tested using PRNT; JE neutralizing antibody titers  $\geq 1:10$  will be considered seroprotective.

After the blood draw at Visit 02 occurring in May to December 2016, four years after their initial vaccination, both groups will receive a single subcutaneous booster dose of CD-JEV. Additional serum samples will be collected on Day 7 and Day 28 following the booster dose for measurement of serum anti-JE neutralizing antibody titers.

Following the booster dose, children will be monitored for immediate reactions during the first 30 minutes, solicited injection site and systemic adverse reactions for 7 days, unsolicited adverse events and serious adverse events for 28 days. All safety events will be identified or observed by study staff during home visits, clinic visits, and/or reported by a parent or legal guardian. Solicited and systemic adverse reactions will be assessed through home visits 1 through 6 days following vaccination, and a fixed site clinic (FSC) visit on Day 7 following vaccination. Information regarding unsolicited AEs occurring in the 28 days following vaccination will be collected and recorded on a standard questionnaire during clinic visits. Events will be graded for severity and assessed for relatedness to vaccination by the investigator.

The study will be open-label; no placebo control will be employed and safety assessments will be unblinded.

[figure not shown]

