  - Name of vaccine given to child.
  - Schedule of visits.
  - Indication that the child is in a vaccine trial and a request that medical personnel who treat the child contact the local PI within the study duration.
- The appropriate section(s) of the CRF will be completed.

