#### **4.4.6. Clinic follow-up visit (Visit 10, 28 days post vaccination $\pm 7$ days)**

A final study visit will be conducted 28 days after booster vaccination. The study team will:

- Inquire about the child's health (any illnesses or medications taken or visits to a healthcare facility).
- Inquire about any adverse events.
- Collect 2 ml of blood from participants with aseptic technique to detect anti-JE serum neutralizing antibody with the PRNT-50.
- Complete the appropriate section(s) of the CRF.
- Exit the participant from the study.

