**7.2.4. Serious adverse events**

An SAE is defined as an AE that meets one of the following conditions:

- Death.
- Life threatening (participant at immediate risk of death). *(The term “life-threatening” in the definition of “serious” refers to an event in which the patient was at risk of death at the time of the event; it does not refer to an event which hypothetically might have caused death if it were more severe.)*
- Requires inpatient hospitalization or prolongation of existing hospitalization.
- Results in a persistent or significant disability or incapacity.
- Important medical events that may not result in death, be life threatening, or require hospitalization may be considered SAEs when, based upon appropriate medical judgment, may jeopardize the participant and may require medical or surgical intervention to prevent one of the outcomes listed in this definition. Medical and scientific judgment should be exercised in deciding whether reporting is appropriate.

All SAEs occurring within 28 days post vaccination must be reviewed and evaluated by a study physician (SAE relationship to study vaccine must be evaluated as outlined in Section 7.2.2) and recorded on an SAE form and reported (as specified in Section 7.3). SAEs, whether serious or not, that persist at the end of the trial will be followed up by the investigator until satisfactory resolution or until the investigator deems the event to be chronic or the participant to be stable. The investigator will document the date of final disappearance of the adverse event

on a data clarification form. All care for SAEs or care required as part of the study will be provided to study participants free of cost.

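### The unsolicited AE endpoint runs to Day 28 after the booster, but the last AE inquiry and study exit may fall from Day 21, and SAP 7.2 does not show or allow for the shorter observation (minor; early exit can only lower the proportion)

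*Protocol*

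**What the plan says.** - **Endpoint.** Protocol 2.4 defines it as "Frequency counts and percentage of participants reporting unsolicited AEs and serious adverse events (SAEs) occurring within 28 days of booster vaccination". SAP 7.1 and 7.2 use the same 28 days.
- **Collection.** Protocol section 4 states: "Information regarding unsolicited AEs occurring in the 28 days following vaccination will be collected and recorded on a standard questionnaire during clinic visits". The same paragraph also names report by a parent or guardian as a way in which safety events are identified.
- **Last inquiry.** Visit 10 is planned for Day 393, which is 28 days after Visit 02, but Protocol Table 4 allows it "21 to 35 days after booster vaccination". The steps listed for this visit in Protocol 4.4.6 end with "Exit the participant from the study". No later contact is scheduled.
- **Passive routes.** Protocol 7.4.1 says: "The parent will also be reminded to contact the study team if the child experiences any illness". Protocol 4.4.5 gives parents a similar reminder at Visit 09. The identification card in Protocol 4.4.3 carries a "request that medical personnel who treat the child contact the local PI within the study duration".
- **SAEs.** Protocol 7.2.4 says "All SAEs occurring within 28 days post vaccination must be reviewed and evaluated by a study physician", and Protocol 7.3.1 says "All SAEs occurring within 28 days post booster dose must be reported". Neither duty depends on the date of Visit 10.
- **Analysis.** SAP 3.1.3 puts every boosted child in the safety set. SAP 7.2 reports the number and proportion with at least one unsolicited AE, with a 95% CI. SAP 3.3.1 works from available data and has rules for missing severity, relationship and dates, but none for fewer than 28 days of observation. SAP 4.2 counts early discontinuations, but a child who completes Visit 10 on Day 21 is not one.

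**The concern.** The endpoint promises 28 days, while a visit schedule followed to the letter can stop asking after 21. An AE that starts after an early exit, before Day 28, and is not volunteered by the family or a treating clinician is recorded as no event, and the child stays in the denominator. A visit on Days 29 to 35 cannot make up for this, because onsets after Day 28 lie outside the endpoint. The loss from this mechanism therefore goes one way, and a confidence interval does not reveal it.

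The booster's safety profile is a secondary objective. What is at stake is the completeness of the unsolicited AE proportion, mainly for milder events, and whether a reader of the report can see how many children were asked about the full 28 days. As planned, no table shows that.

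**Working it through.** **1. The plan's own window.** 393 − 365 = 28 days. 28 − 7 = 21 and 28 + 7 = 35, which agrees with Table 4. At most 7 of the 28 days (25%) go without scheduled inquiry for a child seen within the window.

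**2. Inputs that the documents do not give.** There is no expected AE rate, no distribution of Visit 10 days and no timing of events. I assume a true 28-day proportion p = 10% and no capture after exit. Visit days on 21 to 35 are normal around Day 28 (SD 1 or SD 2), uniform, or all on Day 21.

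**3. Formulas.** Let d be the visit day with weight w(d), m = min(d, 28) and L = −ln(1 − p) = 0.10536.
- Constant hazard: F(t) = 1 − exp(−L·t/28).
- Early clustering with hazard half-life h days: k = ln 2/h, c = L/(1 − exp(−28k)), F(t) = 1 − exp(−c·(1 − exp(−k·t))).
- Observed proportion = Σ w(d)·F(m).

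**4. Worked case: uniform visits, constant hazard.** F on Days 21 to 27 is 7.598, 7.945, 8.291, 8.635, 8.978, 9.320 and 9.661%, which sum to 60.428. The eight days from 28 to 35 each give 10.000%. (60.428 + 80)/15 = 9.362%, a loss of 0.64 points.

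**5. Results for a true 10%.** Losses are in percentage points.

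| Visit days | Seen before Day 28 | Observed, constant hazard | Loss, constant hazard | Loss, h = 7 to 3 days |
|---|---|---|---|---|
| SD 1 | 30% | 9.88% | 0.12 | 0.02 to 0.001 |
| SD 2 | 40% | 9.73% | 0.27 | 0.06 to 0.004 |
| Uniform 21–35 | 47% | 9.36% | 0.64 | 0.15 to 0.01 |
| All on Day 21 | 100% | 7.60% | 2.40 | 0.63 to 0.06 |

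As a check on the last row with h = 7: Day 21 is three half-lives and Day 28 is four, so c = 0.10536/(1 − 1/16) = 0.11238. Then F(21) = 1 − exp(−0.11238 × 7/8) = 9.366%, a relative loss of 6.3%. With h = 3 it is 0.6%. Under constant hazard it is 24%.

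If half of the post-exit AEs are reported anyway, the constant-hazard relative losses of 2.7% (SD 2) and 6.4% (uniform) halve to 1.3% and 3.2%.

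**6. Scale.** With the SAP's 10% to 40% attrition, and assuming all enrolled children are boosted, n is 393 to 590 in Group A (655 × 0.6 to 655 × 0.9) and 98 to 147 in Group B (163 × 0.6 to 163 × 0.9). The Wilson half-width z·√(p(1−p)/n + z²/4n²)/(1 + z²/n) at 10% is 3.0 to 2.4 points in Group A and 6.0 to 4.9 in Group B. In children, the constant-hazard loss among 491 to 736 boosted is 1.3 to 2.0 (SD 2) or 3.1 to 4.7 (uniform).

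**7. SAEs.** At an assumed 1% with no capture, the loss is 0.14 to 0.20 of a child (SD 2) or 0.33 to 0.49 (uniform), before any credit for the 28-day reporting duty.

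**8. Does a censored estimate recover the target?** If exit day is unrelated to AE risk, the product-limit estimate at Day 28, censored at m, returns 10.00% for the SD 1, SD 2 and uniform spreads. If every child left on Day 21, Day 28 could not be estimated.

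**The case against.** The case against acting has several sound parts.

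- **Capture after exit is not nil.** The protocol names parent report as a route, and parents are reminded of it. Zero capture is a worst case. What remains is that reporting after exit is not guaranteed, and that the card's request to treating staff is limited to the study duration.
- **The effect is small.** The study is descriptive, with no hypotheses and no AE threshold, and the losses lie well inside the confidence intervals. That supports a minor rating. It does not remove the gap, because the intervals do not reflect under-ascertainment.
- **The data largely exist.** The SAP provides for onset dates, termination dates and participant-level listings, so days observed should be derivable. What is missing is the table.
- **The visit spread is assumed.** SD 1 fits the documents as well as SD 2 does, and it puts 30% rather than 40% of children before Day 28.

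Four stronger readings are tempting, and the documents do not support them.

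- A reader might infer that all bias in the AE proportion is downward. Only early exit has a fixed direction. The date rule in SAP 3.3.1 can move events either way. For example, with a booster on 20 May and a true onset on 20 June (Day 31), a missing day becomes 15 June (Day 26), so the event enters the window.
- A reader might take 24% as the likely loss. It needs every exit on Day 21, constant hazard and no passive capture, all together.
- A reader might infer that the comparison of Groups A and B is biased. The same window applies to both groups, and nothing suggests different visit timing.
- A reader might call the plan self-contradictory. A visit window and an endpoint window can differ without contradiction. What is absent is a rule for the difference.

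**Conclusion.** The gap stands, at minor severity. The unsolicited AE endpoint covers 28 days, scheduled inquiry may end from Day 21, and SAP 7.2 neither reports nor allows for the shorter observation. Through early exit, the simple proportion can only be too low.

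Confidence is high in the documentary gap and not in any single size. At an assumed true 10% with visits centred on or spread around Day 28, the loss is 0.12 to 0.64 points under constant hazard with no capture after exit, and about 0.15 points or less if events cluster early. It would become substantial only if exits were concentrated near Day 21, events were spread evenly over the window and families rarely reported afterwards. The documents give no reason to expect that combination. SAEs are less affected because the 28-day review and reporting duty is independent of the visit date, although learning of an SAE after exit still depends on the family or the treating clinician.

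**What to change.** In SAP 7.2:

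1. Keep the simple 28-day proportion as planned, over all boosted children.
2. Tabulate by group the number and proportion of boosted children last contacted before Day 28.
3. Add a Day-28 cumulative incidence of first unsolicited AE with a 95% CI, censored at last contact (or at Day 28 if that is earlier). State the assumption that exit day is unrelated to AE risk.
4. Keep AEs passively reported after exit in the simple proportion and the listing, but do not count them in the censored estimate.

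Two shortcuts should be avoided. A per-child-day rate converted to 28 days gives 10.4% to 11.0% for a true 10% when events cluster early. A denominator of children observed to Day 28 plus those with earlier events gives 15.3% to 16.3%. Both ranges cover the SD 2 and uniform spreads.

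The cost is one extra safety table from dates already planned for collection. There are no added participants or blood draws, and the Visit 10 serology window is unchanged. The limitation is that the censored estimate is unavailable if no child is observed to Day 28.

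A safety contact at or after Day 28 for children seen earlier would close the gap at source, but it is a separate option with a real resource cost. Under the assumed spreads it means about 147 contacts (30% of 491) to 343 (46.7% of 736). It is not part of the minimum fix.
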